### CHANGES TO PROTOCOL

This version incorporates the following changes from protocol version 2, dated February 2004.

Change	Details
Contacts page	Trial Co-ordinator, [name] has now been replaced by [name] and [name]
	E-mail addresses and phone numbers updated for [name] and [name]
Page 5	Exclusion criterion has been amended from
	'have undergone chemotherapy/ hormonal therapy for cancer of the contralateral breast (or other sites) in the previous 12 months'
	to read
	'have undergone chemotherapy/ hormonal therapy for cancer of the contralateral breast (or other sites) in the previous 12 months or have chemotherapy planned to any site before their breast surgery.'
Page 6, 8, 16, 19	"12 months post-randomisation " changed to "12 months post-radiotherapy "
Page 40	GP letter version 2 replaced with version 3 – updated to include new contact details

CHANGES TO PROTOCOL

This version incorporates the following changes from protocol version 1, dated June 2001.

Change	Details
All references	NYCTRU changed to CTRU
	Northern and Yorkshire Clinical Trials and Research Unit changed to Clinical Trials Research Unit
	BI-RADS changed to BIRADS
	Telephone contact details for Trials Unit staff and randomisation have changed from [name] to [name]
	The WCTN are no longer acting as the Welsh Co- ordinating Centre for the trial
Contacts page	[name] has replaced [name] as project Manager
	Trial Co-ordinator, [name] has been replaced by [name]
	[name] has been added to the Health Economics contacts
	E-mail addresses and phone numbers updated for [name], [name], [name], [name], [name] and [name]
Page 4	Secondary objectives v) term 'inappropriate mastectomy' changed to 'inappropriate more extensive surgery'
Page 6	"12 months post-radiotherapy" changed to "12 months post randomisation"
Page 8	1.5T changed to high field (1T or 1.5T)
Page 9	Section 6. Specific centres removed.
	1.5T changed to high field (1T or 1.5T)

Page 10	Randomisation number changed from [name] to [name]
Page 11	Question GE3 removed from FACT-B
	7.2 Timing of QOL
	HADS, FACT B, Ad-hoc and EQ5D questionnaires will be sent at 8 weeks post randomisation (not at 4 weeks post initial surgery and 4 weeks post repeat operation/ mastectomy)
Page 14	Means of collection of Histopathology data has been amended to reduce the size of the CRF and make use of data collection already in place.
Page 16	9.2.5 'inappropriate mastectomy' changed to 'inappropriate more extensive surgery', definition altered accordingly
Page 17	10.2 accrual updated
Page 20	'inappropriate mastectomy' changed to 'inappropriate more extensive surgery'
Page 23	WCTN removed.
	Section 15 - Confidentiality statement made more explicit
Page 31	Patient information sheet version 1 replaced with version 2 - Confidentiality statements made more explicit and name changed to CTRU
Page 35	Consent form version 1 replaced with updated consent form version 3 - Confidentiality clause added and name changed to CTRU
Page 37	Consent form 2 version 1 replaced with version 2 – name changed to CTRU
Page 38	Investigator Terms of Reference inserted
Page 40	GP letter version 1 replaced with version 2 – updated to include new contact details

# **1. BACKGROUND**

Currently 14.2% of 50 to 65 year old women with a C5/B5 pre-operative diagnosis undergo more than one operation for primary breast cancer, although the quality assurance standard for the NHS Breast Screening Programme (BASO Specialist Group Meeting, 2000) is < 10% re-operation rate for incomplete tumour excision. Previous studies of surgical treatment for primary breast cancer, without subsequent radiotherapy, have demonstrated an increased risk of local tumour recurrence of 25 to 40% (Leopold et al, 1989; Kurtz et al, 1990), when the initial disease is multi-focal or multicentric, compared with an 11% recurrence rate when the initial tumour is uni-focal. A higher rate of inadequate/ indeterminate resection margins in specimens with multiple malignant foci may account for these findings, but it has also been shown by detailed sectioning of mastectomy specimens that additional tumour foci are present in 30 to 63% of women mammographically suspected of having uni-focal disease. However, when tumour resection margins are clear and radiotherapy administered, similar rates of recurrence are seen in both uni-focal and multi-focal tumour groups (Hartsell et al, 1994; Kurtz, 1996). Therefore a patient's best chance of successful breast conservation appears to depend on accurate preoperative identification and operative management of all local tumour foci.

Malignant lesions are more difficult to detect in the mammographically dense breast because of technical factors including reduced image contrast and unsharpness and the similarity in density between cancer and normal fibroglandular elements. Contrast-enhanced magnetic resonance imaging (MRI) detects neovascularisation induced by malignant lesions and has already been used to good effect to determine the therapeutic approach.

There is now substantial evidence of a good correlation between the findings at MR imaging and histology of resected specimens, with results exceeding those obtained by X-ray mammography or ultrasound (Davies et al, 1996; Balen et al, 1997; Esserman et al, 1999). In 1993 Harmes et al, using a RODEO technique, demonstrated a good correlation between MR findings and histopathology of lesion margins in lumpectomy patients (Harmes et al, 1993). This work was confirmed three years later by Davies et al, who used a 3D fast spoilt gradient echo, contrast-enhanced, fat-suppressed sequence, and demonstrated an excellent correlation between the largest cancer diameter measured by MR and histopathology, compared with poorer correlation coefficients and larger standard errors for X-ray mammography and ultrasound (Davies et al, 1996). Ando and colleagues presented similar data recently which demonstrated a good correlation between histopathology and direct invasion of mammary tissue, satellite nodule formation and intraductal tumour extension (Ando et al, 1997). Current evidence suggests that chest wall invasion can be diagnosed with confidence, and reports from as early as 1986 quote alteration in patient management following MR, secondary to improved loco-regional staging (Deutch et al, 1993; Whitney et al, 1993; Fischer et al, 1994).

Limited reports of the role of dynamic contrast-enhanced magnetic resonance imaging (DCE-MRI) in the clinical management of patients scheduled for breast conservation surgery are available. Tan et al examined 83 patients scheduled for breast conservation therapy and found management to be definitively altered in 18%, with 13% of women undergoing additional surgery (Tan et al, 1999). However, this group was unable to detect factors predictive of alteration in outcome from either patient or tumour characteristics, mammographic results or the timing of MR imaging. In a further larger study in 1999 (463 women with 548 cancers), management was changed in 14.3% of women due to detection of more extensive or multi-centric disease (Fischer et al, 1999). Of the 54 patients

with multi-focal/ multi-centric disease, 48% had breast imaging reporting and data systems (BIRADS) overall breast composition pattern 4, and 52% pattern 3, but no mammographic or ultrasound criterion for defining special subgroups of women with multi-focal or multi-centric disease seen by MR alone were detected.

It is essential that care be exercised in the diagnosis of multi-focal disease, as a preliminary report by Balen et al commented on inappropriate mastectomy in up to 28% of patients (Balen et al, 1997). In a further report by Krämer et al, multiple 3D MR acquisitions obtained at 90-second intervals demonstrated improved sensitivity at 89% compared to 66% for X-ray mammography and 79% for ultrasound, but 17% of women had an incorrect diagnosis of multi-centric disease (Krämer et al, 1997). Of note, both studies utilised 3D imaging of the breast at between 60-90 seconds intervals following bolus injection of the MR contrast agent dimeglumine gadopentetate (Gd-DTPA) and the reduced temporal resolution may have contributed to the false-positive results.

With the detection of increasingly smaller lesions, the specificity of MR imaging becomes crucial to patient management. Currently two approaches have been used to examine contrast uptake characteristics of breast lesions, namely 2D dynamic imaging which allows relatively rapid data acquisition at a limited number of slice locations and 3D high-resolution imaging, with the penalty of increased acquisition time, but with complete coverage of the breast. In addition although the morphological appearance of the lesion may not be diagnostic, spiculation and rim enhancement are highly suggestive of malignancy, whereas a lobulated lesion with internal septations is suggestive of a fibroadenoma. This study employs a compromise by obtaining 'dynamic' data at 45-second intervals using multiple thin slices, which provide full coverage of both breasts, followed by post-contrast, fat-suppressed, high-resolution imaging for morphological information.

The methods of analysis of DCE-MRI data are numerous but empirical techniques are the simplest, least labour-intensive, and the most widely applied. These techniques are used either alone or in combination, to examine contrast uptake relative to background, at pre-determined time points, which have been shown previously to provide best lesion discrimination (Buckley et al, 1994; Gribbestad et al, 1994; Orel et al, 1995; Hulka et al, 1995; Liney and Turnbull, 1999). However these are subject to some inaccuracies resulting from timing and speed of bolus injection and seldom allow for spurious data points secondary to artefacts. Kuhl et al have recently reported on the classification accuracy of experienced radiologists subjectively assessing signal-intensity time curves (Kuhl et al, 1999). These curves were subdivided into those that demonstrated a straight or curved line (Type Ia and b); those with a sharp bend after the initial up slope with plateau thereafter (Type II); and those in which contrast washout was evident after an initial up slope (Type III). Using these criteria the diagnostic efficacy was 86%, with a sensitivity of 91% and a specificity of 83% respectively. This is similar to an earlier report by Knowles et al, who quoted an accuracy rate of 76% for an experienced radiologist using signal intensity time curves alone to differentiate benign from malignant lesions (Knowles et al, 1998). The accuracy value rose to 91% with the addition of morphological information from post-contrast, fat-suppressed images. As a consequence, lesion categorisation in this study relies on both signal intensity time curve evaluation and morphological information (Kuhl et al, 1999).

Controversy exists over the clinical importance of multi-centric foci. Results from correlative radio-pathological studies vary substantially with between 10 to 50% of multi-centric foci reported to be present outwith the index quadrant of the breast (Holland et al, 1985; Vaidya et al, 1996). However most authors agree that more than 90% of early recurrences occur in the index quadrant

whether or not radiotherapy is given (Fisher et al, 1992). As a consequence of these findings some authors argue that small multi-centric foci may not become clinically apparent during a woman's lifetime and that their removal is not necessary (Douek et al, 1998). Indeed others suggest that multi-centric foci may differ from residual tumour in biological potential and hence clinical progression (Sacchini, 1997). However at present the clinical impact of MR-detected multi-centric foci is not known and few surgeons, let alone patients, would condone the deliberate failure to remove all viable cancer in early stage disease to elucidate natural history. This study has reached something of a compromise by choosing to ignore MR-only detected, less than 5 mm in diameter lesions, for which current MR techniques are seldom diagnostic, but biopsying larger lesions prior to definitive surgery.

The cost-effectiveness of MR imaging in this clinical setting is unknown and can only be answered by a randomised controlled clinical trial, which addresses the issues of relative accuracy rates for depicting tumour margins; the uncertainty surrounding pre-operative identification of multi-centric disease, determination of the risk factors for referral for MR imaging; the impact of MR imaging on clinical management, on quality of life and patient satisfaction; and the medium-term ipsilateral breast tumour recurrence rate. Such information will inform those responsible for provision of future health care requirements.

#### 1.1 RATIONALE FOR STUDY DESIGN

The design of this study has been influenced by a number of considerations:

- i) Use of technology which is commonly available in a district general setting.
- ii) Acquisition of data which can be analysed rapidly without specialist physicist input.
- iii) The suggestion by the NHS Health Technology Assessment group for clinical trials to be designed pragmatically, and for multi-centre trials to involve a relatively small number of centres.
- iv) The requirement to provide answers quickly to a technology-driven modification of current surgical practice.
- v) Use of current NHS Breast Screening Programme quality assurance criteria to minimise additional work-load.

# **2.** AIMS AND OBJECTIVES

The overall aim of this randomised controlled trial is to determine the potential benefits to the patient and to the NHS of the addition of MR imaging to the routine techniques employed for loco-regional staging of primary breast cancer.

The primary objective of the study will be to evaluate the role of MR imaging with respect to:

i) Comparison of the repeat operation or mastectomy rates following primary excision between those planned by conventional triple assessment (clinical examination, X-ray mammography and fine needle aspiration cytology/ core biopsy) and those planned by a combination of triple assessment and dynamic contrast-enhanced MR imaging (DCE-MRI). This will include an economic evaluation from a societal perspective of the cost-effectiveness between the two arms.

The secondary objectives of the study will include:

- i) Determination of the ipsilateral breast tumour recurrence rate for both groups up to five years post-diagnosis.
- ii) Comparison of subsequent chemotherapy/ radiotherapy interventions between women planned by triple assessment and those planned by triple assessment and MR imaging combined.
- iii) An assessment of the quality of life and patient satisfaction with management decisions based on either triple assessment or triple assessment combined with MR imaging.
- iv) An investigation of the risk factors for referral for MR imaging. This will be determined by modelling the different and/or combined approaches to the loco-regional staging of primary breast cancer. This will involve multiple regression analysis of baseline information, including demographic data, history of exogenous hormone consumption and concurrent breast disease, data derived from X-ray mammography, ultrasound and MR imaging, and the cytology and histopathology findings.
- v) Evaluation and comparison of the accuracy of loco-regional staging by X-ray mammography, ultrasound and MR imaging, with reference to the tumour extent determined by histopathology of the resected specimens, in particular with respect to more extensive surgery.
- vi) Observation of the percentage of patients in whom a change in clinical management occurs after MR imaging.
- vii) Follow-up of MR-only detected lesions. This will include identification of the false positive mastectomy rate 12 months post-radiotherapy to allow resolution of radiotherapy-induced changes. Only those patients with lesions which were < 5 mm in diameter at diagnosis and not subjected to biopsy, or those with lesions  $\ge 5$  mm in diameter but which were negative on biopsy, will be re-evaluated.

# **3. STUDY DESIGN**

This is a multi-centre, randomised, controlled, open, fixed sample, parallel group trial with equal randomisation, in women with biopsy-proven primary breast cancer who are scheduled for wide local excision following triple assessment (clinical examination, X-ray mammography, fine needle aspiration cytology/core biopsy) and breast ultrasound. Patients will be randomised to receive MR imaging or no further investigations. A pragmatic approach to trial design has been chosen so that results will be generalisable in clinical practice and to reduce unnecessary trial costs that are protocol-driven.

The main trial design will also be supplemented with a qualitative study involving a sample of approximately 100 patients, in order to assess patients' subjective and objective experiences of the treatment process and the care pathway.

# 4. ELIGIBILITY

#### 4.1 INCLUSION CRITERIA

Patients must:

- be aged 18 years or over
- have undergone X-ray mammography (standard medio-lateral oblique, cranio-caudal and where appropriate paddle/ axillary views carried out within the guidelines of the NHS BSP), and ultrasound scanning (using a 7.5 to 13 MHz linear array transducer) during the current treatment episode
- have pathologically documented primary breast carcinoma, either from fine needle aspiration cytology or core biopsy
- be scheduled for wide local excision on the basis of existing results
- provide written informed consent.

#### 4.2 EXCLUSION CRITERIA

Patients will be excluded from this study if they:

- are medically unstable
- have a known contraindication to MR scanning
- are known to have had an allergic reaction associated with previous administration of paramagnetic contrast agent or have a severe allergic diathesis
- require renal dialysis
- have undergone chemotherapy/ hormonal therapy for cancer of the contralateral breast (or other sites) in the previous 12 months or have chemotherapy planned to any site before their breast surgery
- have had surgery or radiotherapy for cancer to the ipsilateral breast
- have had surgery to the ipsilateral breast within the previous 4 months for benign breast disease
- have a history of serious breast trauma within the last 3 months
- are pregnant or breast feeding
- have a disability preventing MR scanning in the prone position
- are under the care of a breast surgeon recruiting into the ALMANAC Trial.

### 5. INVESTIGATIONS AND INTERVENTIONS

#### 5.1 PATIENTS RANDOMISED TO NO MR IMAGING

Patients will receive wide local excision as scheduled. Following wide local excision, patient management and treatment should follow usual practice.

#### 5.2 PATIENTS RANDOMISED TO RECEIVE MR IMAGING

#### 5.2.1 POST RANDOMISATION AND PRE-SURGERY

Women randomised to receive MR imaging should be rapidly assessed so that surgery is not delayed. The MR images should be evaluated by a Consultant Radiologist with prior knowledge of the results of clinical examination, and the results presented to the multi-disciplinary meeting. There are three possible outcomes following review of the mammographic, ultrasound and MR imaging findings:

- a) MR imaging findings are equivalent to X-ray mammography and ultrasound: patients should proceed as planned to wide local excision.
- b) Multi-focal lesion(s)\* are present or the tumour extent is greater than detected on X-ray mammography and/ or ultrasound: surgical management should be reviewed at the multidisciplinary meeting and the patient should proceed to wide local excision or mastectomy as appropriate. In cases of diagnostic difficulty, MR-localized, ultrasound-guided fine needle aspiration cytology or core biopsy should be considered for confirmation of findings.

\* Multi-focal lesions are defined as those located within 2 cms of the index tumour.

c) Multi-centric\* disease is demonstrated by MR imaging: as whole breast coverage during DCE-MRI will require utilization of a 4 mm slice thickness, due to partial volume averaging it is only possible to analyse appropriately lesions of greater diameter than the MR slice thickness. Similarly morphological information from lesions ≤ 4mm in diameter is seldom of clinical utility and reported 'miss' rates for cancer for needle-localised breast biopsy range from 0–7.9% (mean, 2.0%) (Egan et al, 1976; Hermann at al, 1983; Norton et al, 1988; Allen et al, 1994), with some evidence of size dependence (Jackman and Marzoni, 1997). As a consequence a cut-off value of 5 mm has been employed for management purposes as follows:

i) If the multi-centric lesion(s) are < 5 mm in diameter, the patient should proceed as planned to wide local excision.

ii) If the multi-centric lesion(s) are  $\geq 5$  mm in diameter the patient should undergo MR-localised, ultrasound-guided fine needle aspiration cytology/ core biopsy, or if available locally, MR-guided fine needle aspiration cytology/ core biopsy. If the results are:

- **positive** for malignancy, the surgical management should be reviewed and the patient should proceed to wide local excision or mastectomy as appropriate;
- **negative** for malignancy, the patient should proceed as planned to wide local excision;

- indeterminate, the patient should undergo repeat sampling. Patients with indeterminate results on two occasions should proceed according to local protocol, but should undergo repeat MR imaging at 12 months as detailed below;
- **suspicious for malignancy** (i.e. C4 or B4) the surgical management should be reviewed and the patient treated as per local protocols.

\* Multi-centric lesions are defined as those located in a different quadrant of the breast relative to the index tumour.

#### 5.2.2 MR IMAGING AT 12 MONTHS

All patients with lesions < 5mm in diameter or  $\geq$  5mm in diameter and biopsy negative, should undergo repeat DCE-MRI at 12 months post-radiotherapy, to assess persistence of change. Repeat core biopsy/ fine needle aspiration cytology should be carried out for indeterminate/ suspicious enhancing lesions that are  $\geq$  5mm in diameter.

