# Direct line for 24-hour randomisation [name]

Once eligibility has been confirmed and the necessary details obtained, patients will be randomised to receive **MR imaging** or **no further investigations** on a 1:1 basis, and will be allocated a trial number. Patient allocation will use a minimisation algorithm, which will employ the following stratification factors:

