#### Up to 5 years:

- tumour recurrences (date, site and method of diagnosis)
- status (date and cause of death if applicable).

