### **10. STATISTICAL CONSIDERATIONS**

#### **10.1** SAMPLE SIZE

Assuming that the addition of MR imaging will reduce overall repeat operation or mastectomy rates following inadequate wide local excision from approximately 15% to 10%, a total of 1840 patients is required, using a chi-squared test without continuity correction, to detect benefit with 90% power at the 5% (2-sided) significance level (Machin et al, 1997).

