Estimating effects. The key measure of effect for the within-trial cost-effectiveness analysis will be recurrence rates over five years. The within-trial analysis will, therefore, relate differential (societal) costs to differential recurrence rates. Within the trial, patients will also be asked to complete the EQ-5D instrument – a preference-based measure of health status - which will facilitate patient-specific health state values over time (Kind, 1996). Whilst the use of the EQ-5D will facilitate a valuable single-index measure of health within the trial, its main use for the economic evaluation will be to provide health state values (utilities) for the extrapolation modelling (see (i) below). The within-trial cost-effectiveness analysis will include discounting of costs and effects (Department of Health, 1995), adjustment for differential follow-up (Lin et al, 1997) and a stochastic analysis using cost-effectiveness acceptability curves (Van Hout et al, 1994).

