#### **11.2** SECONDARY ENDPOINTS

#### **11.2.1 RECURRENCE RATE**

The analysis of time to ipsilateral breast tumour recurrence will be conducted up to five years post completion of radiotherapy (i.e. when there is at least five years follow-up for all patients). Cox's Proportional Hazards Model will be fitted. Adjustment will be made for the stratification variables and other covariates that are identified as being prognostic of outcome. Treatment effects will be

expressed as hazard ratios. Point estimates will be reported with 95% confidence intervals without formal hypothesis testing, as it is anticipated that the trial will have insufficient power to detect differences between the trial arms in recurrence rates.

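### Ipsilateral recurrence is looked for harder in part of the MR arm than in controls, recurrence is not defined, and neither the Cox comparison nor the cost-effectiveness analysis allows for this

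*Combined protocol and SAP*

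**What the plan says.** The extra scan belongs to the MR arm only, and to a subset of it. Section 5.2.2 covers women whose lesions were under 5 mm, or were 5 mm or more with a negative biopsy; they "should undergo repeat DCE-MRI at 12 months post-radiotherapy, to assess persistence of change". Objective vii in section 2 names the same two groups. Section 5.2.1 adds women whose samples were indeterminate twice. At the 12-month scan, enhancing lesions of 5 mm or more that look indeterminate or suspicious are sampled again. Section 5.1 gives control women usual practice after surgery, with no protocol scan.

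Section 9.2.1 compares five-year local recurrence between arms. In section 11.2.1, "The analysis of time to ipsilateral breast tumour recurrence will be conducted up to five years post completion of radiotherapy", using a Cox model adjusted for the stratification variables and prognostic covariates. The result is a hazard ratio with a 95% confidence interval and no formal test.

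The same outcome drives the economic evaluation, which section 9.1.2 lists as a primary endpoint. In section 11.1.2, "The key measure of effect for the within-trial cost-effectiveness analysis will be recurrence rates over five years". Any difference at five years is then extrapolated to lifetime costs and QALYs.

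Section 8.8 records, at 12 months and again up to five years, "tumour recurrences (date, site and method of diagnosis". No analysis in section 11 uses the method or site. No section, nor the glossary, defines recurrence.

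**The concern.** A between-arm comparison of recurrence assumes that a given cancer is equally likely to be found, and named a recurrence, in either arm. Here a subset of one arm gets a sensitive scan and a biopsy that the other arm does not.

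Two things can follow. First, the scan can find cancer that usual follow-up would not have found within five years. Section 1 itself reports the argument that small multi-centric foci may never become clinically apparent, and cites additional foci in 30 to 63% of women thought on mammography to have uni-focal disease. Control women would carry such foci too, without a protocol scan to show them. Second, a focus seen on the pre-operative MR and left in place may be confirmed as cancer at 12 months. The plan does not say whether that is a recurrence or residual disease.

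The stake lies mainly in the economics. The cost-effectiveness analysis and the extrapolation model use the estimated difference in recurrence itself, so a systematic shift passes straight through to them. A confidence interval does not cover that kind of error.

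**Working it through.** **The plan's own figure.** The only sample size is for repeat operation or mastectomy: "following inadequate wide local excision from approximately 15% to 10%, a total of 1840 patients is required". Section 10.1 bases this on an uncorrected chi-squared test, a two-sided 5% level and 90% power. Per arm,

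n = [1.96·√(2·0.125·0.875) + 1.2816·√(0.15·0.85 + 0.10·0.90)]² / 0.05² = (0.9167 + 0.5977)² / 0.0025 ≈ 917.3.

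This rounds up to 918 per arm, 1836 in total, which agrees with 1840. Allocation is "on a 1:1 basis, and will be allocated a trial number", so there are 920 per arm, giving 90.1% power. The documents state no event count, rate or sample size for recurrence, so nothing there can be reproduced.

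**Inputs below are assumptions.** The documents do not give the share of the MR arm re-scanned (f), the share of those with cancer confirmed (d), or the five-year recurrence rate (r or p). True hazard ratio = 1 throughout.

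**Step 1. Every scan-positive case is an extra event (a maximum).** Extra events = 920·f·d; inflation of the MR-arm count = 1 + f·d/r.

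| f | d | r | Extra events | Factor |
|---|---|---|---|---|
| 5% | 2% | 5% | 0.9 | 1.02 |
| 10% | 5% | 5% | 4.6 | 1.10 |
| 10% | 5% | 3% | 4.6 | 1.17 |
| 20% | 10% | 3% | 18.4 | 1.67 |

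**Step 2. Only cancers that would not otherwise surface within five years are extra.** With a constant hazard, apparent HR = ln(1 − p − f·d)/ln(1 − p), where d is now the net extra yield. For p = 5%, f = 15%, d = 3%: f·d = 0.45 percentage points, 4.1 extra events, MR arm 5.45% against 5.0%, HR = ln(0.9455)/ln(0.95) = 1.09. A wider grid (p 3 to 10%, f 5 to 30%, d 1 to 10%) runs from 1.01 to 2.03. The top value again needs every input at its extreme, including 30% re-scanned.

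**Step 3. Does earlier detection alone move the result, and does classification matter?** A Cox simulation used identical underlying event times in both arms, 5% five-year recurrence, twice the hazard in re-scanned women, a scan at one year with 80% sensitivity, and 60,000 per arm. Uncounted women stayed event-free to five years.

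| Detection lead | Scan-detected cancers | HR, f = 5% | f = 15% | f = 30% |
|---|---|---|---|---|
| up to 3 years | counted | 1.00 | 1.00 | 1.00 |
| up to 6 years | counted | 1.03 | 1.08 | 1.15 |
| up to 3 years | not counted | 0.95 | 0.88 | 0.78 |
| up to 6 years | not counted | 0.94 | 0.84 | 0.71 |

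A three-year lead from a scan at year one reaches only to year four, so every such case surfaces inside the window anyway. The five-year rate is then unchanged. The hazard ratio barely moves, because events are rare and it depends almost entirely on how many there are. With a lead of up to six years, cases from beyond year five are pulled in and the ratio rises. If scan-detected cases are not counted, the ratio falls below 1.

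**Scale.** The 95% confidence interval of the HR spans a factor of exp(1.96·√(2/e)) each way, with e events per arm. At 5% (e = 46) this is 1.50; at 3% (e = 27.6) it is 1.69.

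**The case against.** The plan can be defended on several grounds. Section 11.2.1 makes the recurrence comparison descriptive and admits low power, and section 11 is headed an outline. Section 11.2.7 reports separately on the under-5 mm MR-only lesions at 12 months, so part of the scan's yield will be visible. The trial is pragmatic and analysed by intention to treat, so the repeat scan can be seen as part of the MR pathway. In the middle cases the shift is well inside sampling error.

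All of this is fair, and it limits the size of the concern. It does not remove it. The economic analysis uses the estimate whether or not it is tested. Section 11.2.7 covers one lesion group and does not alter the Cox model. Treating the scan as part of the pathway is a legitimate choice, but then the plan should say so and say how a cancer found by it is counted.

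Three stronger readings are tempting and not supported. A reader might infer that MR-arm women in general are re-scanned; only the groups listed in sections 5.2.1 and 5.2.2 are. A reader might infer that the MR arm's rate and hazard ratio are certainly biased upward; with recurrence undefined, the sign depends on an unstated classification. And a reader might infer that earlier dating alone inflates the result; step 3 shows that it does not when the cancer would have surfaced within five years. Nor need a comparable focus in a control woman stay unseen: it may surface clinically and count.

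**Conclusion.** The concern holds as one of unequal ascertainment, with no definition of recurrence and no planned allowance. The bias is probably upward for the MR arm if scan-detected cancers count as recurrences and some would not have surfaced within five years. It can be downward if they are treated as residual disease and dropped. Neither sign nor size can be settled from the documents.

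The figures are illustrative only. Middle cases give a factor of 1.09 to 1.17, and 1.67 is an upper extreme that requires 20% re-scanned, 10% positive, 3% true recurrence and no overlap with cancers that usual care would find. The point deserves correction because it reaches the primary economic evaluation. The repeat operation or mastectomy comparison and its 1840 patients are unaffected.

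**What to change.** In section 11.2.1:

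- Define ipsilateral recurrence. State how a cancer first found by the section 5.2.2 scan or its biopsy is classified, including one at the site of a lesion recorded on the pre-operative MR. Such sites are known only in the MR arm, so the rule should acknowledge that.
- Using the method, site and date of diagnosis collected under section 8.8, report the five-year rate and hazard ratio by arm (a) with all events and (b) as a sensitivity analysis with scan-detected events handled by one rule stated in advance, for example re-timed or not counted. Note that not counting them can favour the MR arm.
- Identify scan-detected events from all 12-month scans done, including those in twice-indeterminate women.

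In section 11.1.2, carry both versions into the within-trial cost-effectiveness analysis and the extrapolation model, and interpret any difference between arms in the light of both.

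The cost is analysis-plan wording and one extra table, from data already planned. The downside is that recurrence is shown as a range and not as a single figure.
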